5.3.1 Imaging Assessment for the Study

Any incidental findings of potential clinical relevance that are not directly associated with the objectives of the protocol should be evaluated and handled by the Study Investigator as per standard medical/clinical judgment.

5.3.2 Vital Signs, Physical Measurements, and Physical Examination

Vital signs (body temperature, blood pressure and heart rate) will be recorded as outlined in Table 5.1-1, Table 5.1-2, Table 5.1-3, Table 5.1-4, Table 5.1-5, and Table 5.1-6. Blood pressure and heart rate should be measured after the subject has been seated quietly for at least 5 minutes prior to dosing. On Cycle 1 only, the days of elotuzumab dosing, vital signs monitoring should be performed as follows:

- Prior to the start of the elotuzumab infusion
- Thirty minutes after the start of infusion
- At the end of the infusion
- Thirty minutes post completion of the elotuzumab infusion.
- Subjects who experience a Grade ≥ 2 infusion reaction require vital signs to be monitored every 30 minutes for 1- 2 hours (as clinically indicated) after the end of the elotuzumab infusion.

Height will be recorded at screening. Weight will be measured at study visits as indicated in Table 5.1-1, Table 5.1-2, Table 5.1-3, Table 5.1-4, Table 5.1-5, and Table 5.1-6.

A full physical examination will be performed at the screening visit, whereas a targeted exam will occur at Day 1 and during on-treatment up to 3 days prior to dosing and post-treatment visits. A targeted physical examination may be performed by a qualified professional guided by the examiner's observations and/or subject complaints on new or changed conditions, symptoms, or concerns. Targeted physical exam includes assessment of heart, lung, and abdomen.

5.3.3 *Performance Status*

Performance assessment will be performed as indicated in Table 5.1-1, Table 5.1-2, Table 5.1-3, Table 5.1-4, Table 5.1-5, and Table 5.1-6 using ECOG performance scale and criteria as described in Appendix 2.

5.3.4 Laboratory Assessments for Safety

Laboratory assessments for safety will be performed at local laboratories. Safety laboratory assessments are listed in Table 5.3.4-1.

Safety Laboratory Assessments		
	Screening as outlined in Table 5.1-1. Within 14 days of first dose of study drug	Study Visits as outlined in Table 5.1-2,Table 5.1-3, Table 5.1-4, Table 5.1-5, and Table 5.1-6.
Hematology		
CBC	Х	Х
Differential	Х	Х
Platelets	Х	Х
Chemistry		
Sodium	Х	Х
Potassium	Х	Х
Chloride	Х	Х
Albumin	Х	Х
	(within 28 days of first dose of study drug)	
Alkaline Phosphatase	Х	Х
ALT (SGPT)	Х	Х
AST (SGOT)	Х	Х
Total Bilirubin	Х	Х
Lactate Dehydrogenase	Х	Х
BUN (or Urea)	Х	Х
Creatinine	Х	Х
Glucose	Х	Х
Calcium	Х	Х
Pregnancy Test		
Urine or Serum Pregnancy	X (2 tests: one 10 - 14 days prior to the start of study drug and one within 24 hours prior to the start of study drug)	X Pregnancy test must also be performed at end of treatment, and at 30, 60 and 90 days off treatment. The test at 90 days off treatment may be performed locally if the patient is not scheduled to return to the center for other reasons. Urine tests must have a sensitivity of at least 25 IU/L.
Hepatitis B surface antigen (HBV sAg, Australia antigen) and hepatitis C antibody (HCV Ab) or HCV ribonucleic acid (RNA)	X ^a	

Table 5.3.4-1:Safety Laboratory Assessments

Revised Protocol No.: 03 Date: 08-Mar-2018

Safety Laboratory Assessments		
	Screening as outlined in Table 5.1-1. Within 14 days of first dose of study drug	Study Visits as outlined in Table 5.1-2,Table 5.1-3, Table 5.1-4, Table 5.1-5, and Table 5.1-6.
Thyroid stimulating hormone (TSH) (reflex to free T3, free T4 or abnormal result)	X ^a	X ^b

Table 5.3.4-1: Safety Laboratory Assessments

^a Within 28 days of first dose of study drug

^b TSH (reflex to free/total T3, free T4 for abnormal result) to be performed every 2 cycles (\pm 7 days) from first dose regardless of schedule.

5.4 Efficacy Assessments

Efficacy endpoints will be based on analysis of serum and urine electrophoresis (SPEP and UPEP), sFLC (for those with sFLC disease only), corrected calcium (serum calcium and serum albumin), imaging and bone marrow assessments, all at predefined intervals as specified in Table 5.1-1, Table 5.1-2, Table 5.1-3, Table 5.1-4, Table 5.1-5, and Table 5.1-6. Assessments done at local labs versus central labs are indicated in Table 5.1-1, Table 5.1-2, Table 5.1-3, Table 5.1-4, Table 5.1-1, Table 5.1-2, Table 5.1-6. Assessments for SPEP and UPEP and molecular MRD will be based on central lab results, whereas assessments of bone marrow, bone lesions, extramedullary plasmacytomas, and corrected calcium will be based on local analysis at the site.

5.4.1 Primary Efficacy Assessment

Response criteria according to guidelines of the modified IMWG^{33,34} (Appendix 4) will be used for the primary analysis. For the purposes of this study, all subjects' tumor assessments by myeloma laboratory tests should be re-evaluated per the protocol-stated frequency relative to the date of first dose of study drug until disease progression based on the modified IMWG criteria, irrespective of dose delays or treatment cycle. **If subject does not have documented disease progression at time of study drug discontinuation, then tumor assessments should still be performed according to the same schedule described above until disease progression.** Subjects will be followed for survival at least once a year by phone after disease progression.

All efficacy laboratory assessments should be done through the central laboratory, except corrected calcium (serum calcium and serum albumin), and bone marrow assessments for plasma cell percentage and light chain restriction (clonality by IHC or flow cytometry). Only if a subject is unable to come to the site for a visit to have specimens collected for a central lab (especially after study drug discontinuation), a SPEP, UPEP, or sFLC assessment can be performed locally, in lieu of a central lab assessment. M protein quantification or Serum Free Light Chain (sFLC) must be performed. Any laboratory samples analyzed locally, including for efficacy, must be entered on the appropriate CRF/eCRF.

5.4.2 Laboratory Assessments for Myeloma

Subjects who have urine M protein of zero mg/24 hours at baseline, but have measurable serum M-protein, do not have to continue UPEP assessments until SPEP M protein values are undetectable. Assessment of UPEP M protein and urine immunofixation at the time of possible CR/sCR is mandatory, that is negative urine immunofixation is required to fulfill CR/sCR criteria, even in subjects with non-measurable values at baseline. Therefore, when serum immunofixation electrophoresis (SIFE) becomes negative, UPEP and urine immunofixation electrophoresis (UIFE) collection should begin for these subjects. In addition, a UPEP should be collected if clinically warranted (for example, signs of disease progression (eg, anemia) even when SPEP M-protein is stable).

- 1) **Serum**: Serum protein electrophoresis (SPEP) for M protein quantification, immunofixation, and quantitative immunoglobulin assay.
 - a) Immunofixation of serum is required at baseline and to confirm CR regardless of whether measurable M-protein was present at baseline.
 - b) All other serum tests will be followed at each tumor assessment. Confirmation of \geq PR is required on 2 consecutive assessments.
- 2) Urine: 24-hour urine collection electrophoresis for M protein quantification and immunofixation.
 - a) Immunofixation of urine is required at baseline and to confirm CR regardless of whether measurable M-protein was present at baseline.
 - b) All other urine tests will be followed at each tumor assessment Confirmation of \geq PR is required on 2 consecutive assessments.

5.4.3 Imaging Assessments for Myeloma

5.4.3.1 Skeletal Imaging

Skeletal imaging, by conventional radiography or other methods, for bone lesions will be performed within 60 days prior to first dose of study drug in all EPd cohort subjects and within 28 days in the EN Cohort subjects. Skeletal imaging will be performed on study if clinically indicated. Use of conventional or low dose CT scan (ie, of the spine) or MRI bone survey is acceptable. If imaging is performed on treatment for assessment of progression, the site must use the same modality of imaging as used in screening.

5.4.3.2 Assessment of Extramedullary Plasmacytoma

Computed tomography or MRI should be performed at screening, if clinically indicated, to assess for extramedullary plasmacytoma. To minimize unnecessary radiation in myeloma subjects where progression is primarily based on serum and urine M-protein, on study assessments should only be performed if clinically indicated (ie, pain, concern for disease progression), whether or not present at baseline, and at the time of CR/sCR assessment.

A sum of the products of the longest diameters and longest perpendicular diameter for all measurable lesions will be calculated at screening. This sum will be used as the reference for on study assessments by which to characterize the objective tumor response.

All tumor measurements must be made in millimeters. All documented measurable lesions are to be followed throughout the trial. All assessments to be used for tumor response evaluation,

including the baseline assessment, must be performed using the same method for repeat assessment. CT and MRI scanning are the preferable methods of assessment. Conventional CT and MRI should be performed with contiguous cuts of 10 mm or less or with cuts of 5 (or 10) mm if spiral CT scanning is used. Imaging-based evaluation is preferred to evaluation by clinical examination. Evaluation by chest x-ray is less preferable than CT or MRI, and should only be used for well-defined lesions surrounded by aerated lung. Clinical examination is only acceptable when lesions are superficial, such as a skin nodule or palpable lymph node. Skin lesions must be documented by a photograph with a ruler. Ultrasound is not acceptable for documentation of measurable disease.

Duplicate copies of all imaging studies used for tumor response evaluation will be made available for review by the Sponsor upon request.

Measurable disease are lesions that can be accurately measured in 2 dimensions and both diameters must be ≥ 20 mm when evaluated by standard CT scanning or ≥ 10 mm when evaluated by spiral CT scanning or MRI. The minimum diameter size should be at least twice the slice thickness.

Non-measurable disease are all other lesions (or sites of disease), including those that are too small (ie, do not meet above criteria), occur within a previously irradiated area (unless they are documented as new lesions since the completion of radiation therapy), bone lesions, leptomeningeal disease, ascites, pleural or pericardial effusion (exception for effusions documented by cytology as not malignant or present at baseline without progression), lymphangitis cutis/pulmonis, abdominal masses that are not pathologically/cytologically confirmed and followed by imaging techniques, and cystic lesions.

5.4.4 Definitions of Response and Progression Criteria

See Appendix 4 for definitions of response and progression. All criteria are derived from IMWG,^{33,34} except for minor (minimal) response, which is derived from the European Society for Blood and Marrow Transplantation (EBMT). All response categories require 2 consecutive assessments made before initiation of any new therapy.

Revised Protocol No.: 03 Date: 08-Mar-2018

5.7 Outcomes Research Assessments

Not applicable

5.8 Other Assessments

5.8.1 Pharmacogenomic/Pharmacogenetic Assessments

Genetic assessment (FISH) of myeloma cells is optional and will be performed by a central laboratory on the fresh bone marrow, during the screening period. If a fresh aspirate is not available, but local genetic assessment has been performed, these results must be entered into the CRF/eCRF. This assessment is considered to be standard of care for myeloma. Aspirates obtained will be used to identify prognostic cytogenetic markers that may include: t(4;14), t(14;16), t(11;14), t(6;14), t(14;20), 1q gains/amp, del(17p), del(1p), and del(13).

6. ADVERSE EVENTS

An *Adverse Event (AE)* is defined as any new untoward medical occurrence or worsening of a preexisting medical condition in a clinical investigation subject administered study drug and that does not necessarily have a causal relationship with this treatment. An AE can therefore be any unfavorable and unintended sign (such as an abnormal laboratory finding), symptom, or disease temporally associated with the use of study drug, whether or not considered related to the study drug.

The causal relationship to study drug is determined by a physician and should be used to assess all adverse events (AE). The causal relationship can be one of the following:

Related: There is a reasonable causal relationship between study drug administration and the AE.

Not related: There is not a reasonable causal relationship between study drug administration and the AE.

The term "reasonable causal relationship" means there is evidence to suggest a causal relationship.

Adverse events can be spontaneously reported or elicited during open-ended questioning, examination, or evaluation of a subject. (In order to prevent reporting bias, subjects should not be questioned regarding the specific occurrence of one or more AEs.)

6.1 Serious Adverse Events

A Serious Adverse Event (SAE) is any untoward medical occurrence that at any dose:

- results in death
- is life-threatening (defined as an event in which the subject was at risk of death at the time of the event; it does not refer to an event which hypothetically might have caused death if it were more severe)
- requires inpatient hospitalization or causes prolongation of existing hospitalization (see **NOTE** below)
- results in persistent or significant disability/incapacity
- is a congenital anomaly/birth defect

• is an important medical event (defined as a medical event(s) that may not be immediately lifethreatening or result in death or hospitalization but, based upon appropriate medical and scientific judgment, may jeopardize the subject or may require intervention [eg, medical, surgical] to prevent one of the other serious outcomes listed in the definition above.) Examples of such events include, but are not limited to, intensive treatment in an emergency room or at home for allergic bronchospasm; blood dyscrasias or convulsions that do not result in hospitalization.) Potential drug induced liver injury (DILI) is also considered an important medical event. (See Section 6.6 for the definition of potential DILI.)

Suspected transmission of an infectious agent (eg, pathogenic or nonpathogenic) via the study drug is an SAE.

Although pregnancy, overdose, cancer, and potential drug induced liver injury (DILI) are not always serious by regulatory definition, these events must be handled as SAEs. (See Section 6.1.1 for reporting pregnancies).

Any component of a study endpoint that is considered related to study therapy (eg, death is an endpoint, if death occurred due to anaphylaxis, anaphylaxis must be reported) should be reported as SAE (see Section 6.1.1 for reporting details).

NOTE:

The following hospitalizations are not considered SAEs in BMS clinical studies:

- a visit to the emergency room or other hospital department < 24 hours, that does not result in admission (unless considered an important medical or life-threatening event)
- elective surgery, planned prior to signing consent
- admissions as per protocol for a planned medical/surgical procedure
- routine health assessment requiring admission for baseline/trending of health status (eg, routine colonoscopy)
- medical/surgical admission other than to remedy ill health and planned prior to entry into the study. Appropriate documentation is required in these cases
- admission encountered for another life circumstance that carries no bearing on health status and requires no medical/surgical intervention (eg, lack of housing, economic inadequacy, caregiver respite, family circumstances, administrative reason).
- admission for administration of anticancer therapy in the absence of any other SAEs (applies to oncology protocols)

6.1.1 Serious Adverse Event Collection and Reporting

Sections 5.6.1 and 5.6.2 in the Investigator Brochure (IB) represent the Reference Safety Information to determine expectedness of serious adverse events for expedited reporting. Following the subject's written consent to participate in the study, all SAEs, whether related or not related to study drug, must be collected, including those thought to be associated with protocol-specified procedures. All SAEs must be collected that occur during the screening period and within

100 days of discontinuation of dosing. If applicable, SAEs must be collected that relate to any later protocol-specified procedure (eg, a follow-up skin biopsy).

The Investigator must report any SAE that occurs after these time periods and that is believed to be related to study drug or protocol-specified procedure.

An SAE report must be completed for any event where doubt exists regarding its seriousness.

If the investigator believes that an SAE is not related to study drug, but is potentially related to the conditions of the study (such as withdrawal of previous therapy or a complication of a study procedure), the relationship must be specified in the narrative section of the SAE Report Form.

SAEs, whether related or not related to study drug, and pregnancies must be reported to BMS (or designee) within 24 hours of awareness of the event. SAEs must be recorded on the SAE Report Form; pregnancies on a Pregnancy Surveillance Form (electronic or paper forms). The preferred method for SAE data reporting collection is through the eCRF. The paper SAE/pregnancy surveillance forms are only intended as a back-up option when the eCRF system is not functioning. In this case, the paper forms are to be transmitted via email or confirmed facsimile (fax) transmission to:

SAE Email Address: Refer to Contact Information list.

SAE Facsimile Number: Refer to Contact Information list.

For studies capturing SAEs through electronic data capture (EDC), electronic submission is the required method for reporting. In the event the electronic system is unavailable for transmission, paper forms must be used and submitted immediately. When paper forms are used, the original paper forms are to remain on site.

SAE Telephone Contact (required for SAE and pregnancy reporting): Refer to Contact Information list.

If only limited information is initially available, follow-up reports are required. (Note: Follow-up SAE reports must include the same investigator term(s) initially reported.)

If an ongoing SAE changes in its intensity or relationship to study drug or if new information becomes available, the SAE report must be updated and submitted within 24 hours to BMS (or designee) using the same procedure used for transmitting the initial SAE report.

All SAEs must be followed to resolution or stabilization.

6.2 Nonserious Adverse Events

A *nonserious adverse event* is an AE not classified as serious.

6.2.1 Nonserious Adverse Event Collection and Reporting

The collection of nonserious AE information should begin at initiation of study drug until 60 days from the last dose of study drug for patients in the EPd cohort and until 100 days from the last dose of study drug for the EN cohort. Subjects in the EN cohort who cross-over to the EPd cohort but discontinue treatment within 2 cycles of EPd treatment will still need to undergo 100 day follow-

up visit from last dose of the nivolumab to evaluate safety events related to study treatment. Nonserious AE information should also be collected from the start of a placebo lead-in period or other observational period intended to establish a baseline status for the subjects.

Nonserious AEs should be followed to resolution or stabilization, or reported as SAEs if they become serious (see Section 6.1.1). Follow-up is also required for nonserious AEs that cause interruption or discontinuation of study drug and for those present at the end of study treatment as appropriate. All identified nonserious AEs must be recorded and described on the nonserious AE page of the CRF/eCRF (paper or electronic).

Completion of supplemental CRF/eCRFs may be requested for AEs and/or laboratory abnormalities that are reported/identified during the course of the study.

6.3 Laboratory Test Result Abnormalities

The following laboratory test result abnormalities should be captured on the nonserious AE CRF/eCRF page or SAE Report Form (paper or electronic) as appropriate:

- Any laboratory test result that is clinically significant or meets the definition of an SAE
- Any laboratory test result abnormality that required the subject to have study drug discontinued or interrupted
- Any laboratory test result abnormality that required the subject to receive specific corrective therapy.

It is expected that wherever possible, the clinical rather than laboratory term would be used by the reporting investigator (eg, anemia versus low hemoglobin value).

6.4 Pregnancy

If, following initiation of the study drug, it is subsequently discovered that a female study subject or female partner of male study subject is pregnant or may have been pregnant at the time of investigational product exposure, including during the time to washout (90 days) plus one ovulatory cycle (30 days) for a total of 5 months after product administration (female study subjects); or plus one spermatogenesis cycle (90 days) for a total of 7 months after product administration (female partners of male study subjects), the investigator must immediately notify the BMS Medical Monitor/designee of this event and complete and forward a Pregnancy Surveillance Form to BMS Designee within 24 hours and in accordance with SAE reporting procedures described in Section 6.1.1.

In most cases, the study drug will be permanently discontinued in an appropriate manner (eg, dose tapering if necessary for subject safety).

In the rare event that the benefit of continuing study drug is thought to outweigh the risk, after consultation with BMS, the pregnant subject may continue study drug after a thorough discussion of benefits and risk with the subject.

The investigator must immediately notify the BMS (or designee) Medical Monitor of this event and complete and forward a Pregnancy Surveillance Form to BMS (or designee) within 24 hours
of awareness of the event and in accordance with SAE reporting procedures described in Section 6.1.1.

Follow-up information regarding the course of the pregnancy, including perinatal and neonatal outcome and, where applicable, offspring information must be reported on the Pregnancy Surveillance Form.

Any pregnancy that occurs in a female partner of a male study participant should be reported to BMS. Information on this pregnancy will be collected on the Pregnancy Surveillance Form.

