3.5 Discontinuation of Subjects following any Treatment with Study Drug

Subjects MUST discontinue investigational product (and non-investigational product at the discretion of the investigator) for any of the following reasons:

- Subject's request to stop study treatment
- Any clinical adverse event (AE), laboratory abnormality or intercurrent illness which, in the opinion of the investigator, indicates that continued participation in the study is not in the best interest of the subject
- Termination of the study by Bristol-Myers Squibb (BMS) or meeting the criteria for stopping rules for cohort(Section 4.5.10).
- Loss of ability to freely provide consent through imprisonment or involuntary incarceration for treatment of either a psychiatric or physical (eg, infectious disease) illness
- Pregnancy (Subjects must discontinue the study drugs.
- Progressive Disease (Appendix 4)
- Subjects who receive any non-protocol specified systemic anti-myeloma therapy before documented progression will be discontinued from all study treatment (including pomalidomide/dexamethasone); however, tumor assessments will continue at 4 week intervals until documented progression.
- Subjects experiencing a Grade 4 infusion reaction related to elotuzumab must discontinue elotuzumab (refer to the Grade 4 Infusion Reaction subsection presented in Section 4.5.5) Subjects may continue pomalidomide and dexamethasone treatment.
- Subjects experiencing a Grade 3 or 4 infusion reaction related to nivolumab must discontinue nivolumab (only).
- Subjects experiencing angioedema, Grade 4 rash, exfoliative or bullous rash, Stevens-Johnson syndrome, or toxic epidermal necrolysis related to pomalidomide must discontinue pomalidomide. Subjects may continue elotuzumab and dexamethasone.
- Subjects experiencing a 56 day delay in all study drugs (elotuzumab, nivolumab, pomalidomide, and dexamethasone) due to an adverse event(s) related to study treatment must be discontinued from study drug. Subjects experiencing delays unrelated to study therapy, for example due to radiation therapy may delay study treatment up to 84 days. Further delays may be allowed after discussion with the medical monitor.

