In the case of pregnancy, the investigator must immediately notify the BMS Medical Monitor/designee of this event, and treatment with the IMPs would immediately be stopped. In most cases, the study drug will be permanently discontinued in an appropriate manner. Please call the BMS Medical Monitor within 24 hours of awareness of the pregnancy. If the investigator

determines a possible favorable benefit/risk ratio that warrants continuation of study drug (ie, allowing restart of study drug if the patient choses to terminate the pregnancy), a discussion between the investigator and the BMS Medical Monitor/designee must occur so that permission can be granted.

All subjects who discontinue study drug should comply with protocol-specified follow-up procedures outlined in Section 5. The only exception to this requirement is when a subject withdraws consent for all study procedures including post-treatment study follow-up or loses the ability to consent freely (ie, is imprisoned or involuntarily incarcerated for the treatment of either a psychiatric or physical illness).

If study drug is discontinued prior to the subject's completion of the study, the reason for the discontinuation must be documented in the subject's medical records and entered on the appropriate case report form (CRF/eCRF) page.

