4. STUDY DRUG

Study drug includes both Investigational [Medicinal] Product (IP/IMP) and Non-investigational [Medicinal] Product (Non-IP/Non-IMP) and are listed in Table 4.-1.

Product Description / Class and Dosage Form	Potency	IMP/Non-IMP	Blinded or Open Label	Packaging / Appearance	Storage Conditions (per label)
Elotuzumab Powder for Solution for Infusion	300 mg/vial or 400 mg/vial	IMP	Open Label	Vial	Refer to the label on the container and/or the pharmacy manual.
Nivolumab Solution for Injection	100 mg (10 mg/mL)	IMP	Open label	Vial	Refer to the label on the container and/or the pharmacy manual.
Dexamethasone Tablets	2 mg and 4 mg and various strengths	Non-IMP	Open-label	Various packing configurations	Refer to label on container or package insert / summary of product characteristics
Dexamethasone Solution	4 mg/mL, 8 mg/mL and various strengths	Non-IMP	Open-label	Various packing configurations	Refer to label on container or package insert / summary of product characteristics
Pomalidomide Capsules	1 mg, 2 mg, 3 mg and 4 mg	IMP	Open label	Various packing configurations	Refer to label on container or package insert

Table 4.-1:Study Drugs for CA204142

Pomalidomide (Pomalyst®), Dexamethasone tablets and solution for IV infusion will be obtained by the investigating site's standard prescribing procedures.

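### Section 6.4 lets a still-pregnant subject continue study drug, whereas Section 3.5 stops the investigational products at once and confines its exception to restart after termination; no precedence is stated

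*Protocol*

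**What the plan says.** Protocol Section 3.5 opens its list of discontinuation reasons with "Subjects MUST discontinue investigational product (and non-investigational product at the discretion of the investigator) for any of the following reasons". One entry reads "Pregnancy (Subjects must discontinue the study drugs". The text after the list says that in the case of pregnancy the Medical Monitor is notified and "treatment with the IMPs would immediately be stopped". It makes permanent discontinuation the usual outcome, then gives an exception. If the investigator sees a possibly favorable benefit/risk ratio that "warrants continuation of study drug (ie, allowing restart of study drug if the patient choses to terminate the pregnancy", a discussion with the Medical Monitor "must occur so that permission can be granted".

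Protocol Section 6.4 also makes permanent discontinuation the usual outcome and requires immediate notification of the Medical Monitor. Its exception is different. In rare cases where benefit is judged to exceed risk, and after the sponsor is consulted, "the pregnant subject may continue study drug after a thorough discussion of benefits and risk with the subject".

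Protocol Section 4 sets the scope of the term: "Study drug includes both Investigational [Medicinal] Product (IP/IMP) and Non-investigational [Medicinal] Product (Non-IP/Non-IMP". Table 4.-1 lists elotuzumab, nivolumab and pomalidomide as IMPs and dexamethasone as the only non-IMP. Section 4.3.3 describes pomalidomide as a thalidomide analogue and warns of birth defects or fetal death if it is taken in pregnancy.

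**The concern.** Both sections are current text, and both govern the same event. Under 3.5 the IMPs are stopped and can return only by way of a restart. Under 6.4 they can continue in a subject who is still pregnant. The protocol does not rank the sections, and neither refers to the other on this point. An investigator or Medical Monitor who relied on 6.4 could therefore agree to something that 3.5 rules out.

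The stakes concern subject and fetal safety, not inference. A subject in the EPd cohort, or one who has crossed over from EN, is on pomalidomide, and the 6.4 sentence does not exempt it. An EN subject before crossover receives no pomalidomide, but the same disagreement applies to elotuzumab and nivolumab.

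**Working it through.** The plan gives no figure here to reproduce. The check is a comparison of the two rules.

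| Question | Section 3.5 | Section 6.4 |
|---|---|---|
| Default | Mandatory discontinuation; IMPs stopped immediately | Permanent discontinuation in most cases |
| Is a stop required before the exception can apply? | Yes: the exception is a restart | No |
| Must the pregnancy end? | Yes, on the wording: the patient chooses termination | No: the sentence refers to a pregnant subject |
| Who agrees? | Medical Monitor, by giving permission | Sponsor is consulted; benefit and risk are discussed with the subject |
| Any drug excluded from the exception? | Not separately; all IMPs are stopped first | None |

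1. *Does the qualifier about most cases in 3.5 soften the stop?* No. It qualifies whether discontinuation is permanent. The immediate stop is stated separately and without qualification.
2. *Does the word continuation in 3.5 cover dosing during pregnancy?* Not as written. It is followed by *ie*, which defines it as restart if the patient terminates the pregnancy. Restart presupposes a stop.
3. *Does 6.4 cover dosing during pregnancy?* Yes. The person who may continue is described as pregnant, and the verb is continue.
4. *Which drugs are affected?* Table 4.-1 lists four drugs: three IMPs and one non-IMP. On the plain wording, the IMPs that may be given during pregnancy number 0 of 3 under 3.5 and up to 3 of 3 under 6.4. Any one subject is on two IMPs: elotuzumab with pomalidomide (EPd or crossed over), or elotuzumab with nivolumab (EN). This count shows the scope of the wording. It is not an estimate of how many subjects are affected.
5. *Does another section settle it?* Only in part. Appendix 6 requires immediate discontinuation on a positive test and bars dispensing to a pregnant patient, which agrees with 3.5. But it limits itself to clinical-supply pomalidomide, and Section 4 says pomalidomide is obtained through the sites' usual prescribing. It may therefore apply to few subjects or none.

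**The case against.** The best defense is that the two sections share a structure: discontinuation as the norm, a rare benefit/risk exception, and sponsor involvement. On that view the conflict rests on one parenthetical in 3.5, where *ie* may have been written loosely for *eg*, since restart after a stop is an odd definition of continuation. The sections could then be read in sequence: stop and notify under 3.5, then agree any exception under 6.4. Pomalidomide is also controlled elsewhere. Sections 1.5, 3.3.1 and 4.3.3 make compliance with a risk-management program a condition of participation and limit supply to one cycle at a time.

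Part of this stands. Harm is unlikely, and the 3.5 sentence is loosely worded and needs amending too. But if *eg* was meant, 3.5 is itself unclear on a fetal-safety rule, so a correction is still needed. The sequential reading does not remove the disagreement about what may finally be agreed. For commercial supply, the documents do not set out what the program requires on a positive test during treatment, and a pomalidomide program does not address the antibodies.

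Two stronger readings are tempting and are not supported:

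- *A site could keep dosing on its own authority when a Day 1 test is positive.* Pregnancy tests do fall within 24 hours before Day 1 dosing (Table 5.1-3). But 6.4 requires immediate notification and allows continuation only after the sponsor is consulted, and it does not say that dosing proceeds meanwhile. The gap is in what the sponsor may agree to, not in what the site does that day.
- *The tapering wording in 6.4 is a second conflict.* The drug is to be "discontinued in an appropriate manner (eg, dose tapering if necessary for subject safety". That is a conditional example, and 3.5 already leaves the non-IMP, dexamethasone, to the investigator's discretion. The ban on reducing elotuzumab or nivolumab in Section 4.5.9.1 sits under guidance on dose modification for toxicity. This wording can stay.

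**Conclusion.** The inconsistency is real and should be corrected. As written, Section 6.4 permits, with sponsor consultation, dosing of an IMP in a pregnant subject, and Section 3.5 does not. The conclusion rests on giving *ie* in 3.5 its ordinary meaning and on the Section 4 definition of study drug.

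The practical size is small. The protocol treats continuation as rare, the number of women of childbearing potential is not given, and sponsor consultation and the distribution program lower the chance of exposure further. The documents do not support a claim that fetal exposure is likely. Nor is there any effect on the primary endpoints, power or analyses. The case for acting is that the possible harm is serious and the two rules cannot both be followed once an exception is sought for a subject who is still pregnant.

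**What to change.** - *Section 6.4:* delete the sentence that lets a pregnant subject continue. Replace it with a cross-reference to Section 3.5, stating that all IMPs (elotuzumab, nivolumab, pomalidomide) are stopped immediately and that none is given while the subject is pregnant.
- *Both sections:* state that restart may be considered only once the subject is no longer pregnant, and only with Medical Monitor permission.
- *Section 3.5:* reword the parenthetical to match. Taken literally it makes elective termination the only route back to treatment and shuts out restart after miscarriage or delivery.

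This keeps the protocol's own stricter rule and its permission step. The cost is a few sentences in two sections, with no added visits, procedures or subjects and no change to the SAP.
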